EFFECT OF HYPERBARIC OXYGEN THERAPY ON THE DEVELOPMENT OF AIRWAY STENOSIS IN PATIENTS WITH SEVERE AIRWAY EXUDATIVE PLAQUES EARLY AFTER LUNG TRANSPLANTATION

[name], [name], [name]

NCT02363959

BACKGROUND:

Central airway stenosis (CAS) is seen in 8-15% patients after lung transplantation.^{1,2} Development of airway stenosis can cause decline in pulmonary function, increased respiratory symptoms, increased infections, and occasionally death³. The lungs are unique in containing dual circulatory supply from the pulmonary circulation which is reanastomosed during lung transplantation, and the bronchial circulation which is not. Perfusion of the large airways is thought to occur via retrograde flow from vascular plexus' between the bronchial and pulmonary arterial circulation until new collateral circulation to the bronchial arterial system can develop in the weeks following transplantation³. Assessment of large airways perfusion has been surprisingly poorly studied, but development of airways ischemia post-transplantation is thought to be involved with development of CAS and other airway complications, opportunistic infections, particularly fungal infections, and possibly with chronic allograft rejection.^{1,4}

CAS is managed with balloon dilation followed by airway stent placement for recurrent stenosis.⁴⁻⁷ A limited number of retrospective studies have shown that the treated airway complications do not affect survival.^{1,8} However, these airway complications prolong mechanical ventilation, hospital and ICU length of stay, increase cost, and adversely affect quality of life³.

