The objective of this study is to evaluate the effect of HBOT on subsequent airway complications in lung transplant recipients with evidence of ischemic changes in the large airway epithelium. Study subjects with extensive desquamation (exudative plaques) of the large airway epithelium in the early post-transplant period will be randomized to HBOT or usual care and followed clinically for 12 months following randomization. We hypothesize that HBOT will decrease the number of airway complications in the treated subjects.

SUBJECT ENROLLMENT

Standard post-lung transplantation care includes a bronchoscopy with transbronchial lung biopsy at 1 month after surgery. We believe that it is in this early period, when the neovascularization of the large airways is thought to occur, that subjects are most likely to benefit from HBOT. Patients who are noted to have extensive exudative plaques (grade 3 or 4) at their 1 month bronchoscopy will be referred for a standard follow-up bronchoscopy 2 to 3 weeks later. Should the patient show no sign of improvement in their airways, or worsening of the plaques they will be considered eligible for enrollment in the study.

Exclusion Criteria

Exclusion criteria include: use of mechanical ventilation with FiO₂ greater than 40%, use of extracorporeal membrane oxygenation, use of inhaled nitric oxide, presence of pneumothorax, pregnancy, or inability to provide informed consent. In addition, subjects who are deemed to be

too clinically unstable to be transported safely to the hyperbaric facility by their treating physicians will be excluded from enrollment.

Randomization

Once subjects are deemed eligible for enrollment, they will be questioned as to their interest in participating in the study by the treating physician. Those interested will be approached by the study coordinator for informed consent. Once informed consent is obtained, subjects will be randomized to usual care or HBOT by selection of a pre-prepared envelope containing the randomization assignment. We will target a total enrollment of 40 subjects with 1:1 enrollment to either HBOT or usual care.

Subject Compensation

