While the patients randomized to receive usual care will not undergo HBOT, both study groups will receive standard serial bronchoscopies for airway clearance and for the collection of bronchoalveolar lavage fluid for culture data, due to the high rate of infection in lung transplant patients. All subjects will undergo the standard surveillance bronchoscopies every 3 to 4 weeks (x3) for clearance of the exudate from the airway, as well as monitoring progression of the airway abnormalities. Additional bronchoscopies will be performed as clinically indicated. Following the completion of the airway surveillance, subjects will revert to the standard rejection surveillance schedule of bronchoscopy every 3 months for the first year post-transplant.

At each surveillance bronchoscopy, subjects will have the standard bronchoalveolar lavage performed for detection of infectious agents. Due to the high evidence of airway infections in patients with severe exudative plaques, a lavage is performed during each bronchoscopy as a part of standard practice to collect microbiologic data. As participants in this study, an, endobronchial biopsy of the airway epithelium will be performed at the main carina to collect a sample of recipient epithelium as well as at the first subcarina for each donor lung. Three samples will be collected from each of the biopsy sites. These samples are small (1 to 2 mm) and are thought to have a minimal clinical risk of minor bleeding associated with the procedure. Biopsy will add roughly 3 minutes total to each procedure. These samples will be used for mRNA extraction to detect expression of genes associated with response to tissue hypoxia.

Measurements and Data Collection

Primary outcomes: Need for airway stent placement and rate of acute rejection in the 12 months of observation as determined by transbronchial lung biopsy.

Secondary outcomes: Include development of airway stenosis, need for balloon bronchoplasty, development of clinically significant pulmonary infection as defined by initiation of antimicrobials to treat the suspected organism, development of airway dehiscence following enrollment in the study, development of bronchiolitis obliterans syndrome, and bronchial epithelial gene expression.

Additional clinical data to be collected will include spirometric data, frequency of hospitalization, hospital days, ICU days, mechanical ventilation days, need for tracheostomy, and survival.

TREATMENT ARM CROSSOVER

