Should patients enrolled in the usual care arm develop airway complications such as airway stenosis, dehiscence, or airway malacia, or if the patient fails to improve their exudative plaque score over the period of observation, they may be offered hyperbaric therapy with continued collection of clinical data. Subjects will be eligible for crossover therapy between 8 and 12 weeks after the initial study bronchoscopy.

There are two criteria for a patient to qualify for HBOT crossover treatment. The first criterion is the development of an airway complication, most likely airway stenosis requiring intervention. This is clinically defined by our group as an airway that is no longer traversable with a therapeutic (6.4mm OD) bronchoscope. Other complications are airway dehiscence or malacia (excessive loss of structural integrity). The second criterion is failure of the airway exudate to improve in score severity during the 8 week observation period. This is measured using the scoring system outlined in Table 1.

RISK/BENEFIT ASSESSMENT

It is currently unknown if treatment of patients with severe exudative plaques in the early post-lung transplant period with HBOT will prevent development of large airway complications. Our limited anecdotal experience suggests it may improve outcomes. The risks of the procedure are small and detailed above. The potential benefits are significant since airway stenosis can lead to worse allograft function, increased infections, and occasionally death. Subjects randomized to usual care will be at usual risk of airway complications. Given the clinical equipoise regarding HBOT treatment in lung transplant, we feel this is an ethical treatment decision for this patient population.

COST TO THE SUBJECT

There will be no additional costs to the subject over usual care. The hyperbaric treatment will be provided at no charge to the subjects.

DATA ANALYSIS AND STATISTICAL CONSIDERATIONS

Data analysis will be performed by the primary investigators. Categorical data will be analyzed using Fisher's exact test given the small sample size, while continuous data will be assessed for statistical significance with Student's t-test. Our prior work with airway stenosis in lung transplant recipients documented a 15% rate of stenosis in all transplant patients. Our clinical experience suggests a rate 2 to 4-fold higher in patients with severe ischemic desquamation of

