the large airways. Experience with HBOT in this population is limited, but rates of significant airway stenosis may be as low as 10% after therapy. Sample size calculations using a 60% stenosis rate in the usual care group, a 10% stenosis rate in the HBOT group with a p-value of 0.05 suggest that a sample of 14 subjects/group will have an 80% power to detect statistical significance. We will target a total of 40 subjects to allow for subject withdrawal and loss due to the development of critical illness in this tenuous population. Intention to treat analysis will be used for all patients based on initial randomization, with subgroup analysis for the crossover patients for airway stent placement. All biologic samples will be collected by week 6, prior to any patient crossover events.

DATA and SAFETY MONITORING

Data will be stored on a secured Access database located on the PIN station “U” drive in an secured folder. All subject entries will be de-identified using a study assigned identification number. The key to the study identifiers will be kept in a locked file cabinet in the study coordinators office. Database use will be limited to the primary investigators, co-investigators, and the study coordinator.

Primary risks are related to bronchoscopy with minimal risk of bleeding related to the endobronchial lung biopsy, and some discomfort from the bronchoscopy itself which is part of usual post-transplant care. Additional risks of hyperbaric treatment are detailed above and very rare. Any adverse events that occur during the study will be immediately reported to the IRB.

Table 1. Pseudomembrane Scoring System

Stage	Definition
Stage 0	No exudate
Stage 1	Limited to anastomosis
Stage 2	Anastomosis to upper lobe orifice, including medial bronchus intermedius
Stage 3	Involvement of the lower lobe orifice
Stage 4	Covers all visible airways

REFERENCES:

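### Spirometry is left to an unadjusted t-test; adjusting for a pre-randomisation value would be a cheap gain in precision on a supportive measure

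*Combined protocol and SAP*

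**What the plan says.** The combined protocol and SAP sets its methods out briefly under Data Analysis and Statistical Considerations. Categorical data go to Fisher's exact test; for the rest, "continuous data will be assessed for statistical significance with Student's t-test". Nothing there or elsewhere mentions a covariate, change from baseline, ANCOVA or a repeated-measures model.

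Spirometry appears under Measurements and Data Collection, after the primary and secondary outcomes: "Additional clinical data to be collected will include spirometric data, frequency of hospitalization, hospital days, ICU days" and further items. No spirometric measure, analysis time point or pre-randomisation measurement is named.

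Under Randomization the target is stated as "We will target a total enrollment of 40 subjects with 1:1 enrollment to either HBOT or usual care", which is 20 per arm. The analysis is by intention to treat according to initial randomisation. The only sample size calculation concerns stenosis, a binary outcome. No power or detectable difference is given for any continuous measure.

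**The concern.** Lung function is tied to the disease process in the plan's own Background: "Development of airway stenosis can cause decline in pulmonary function". Decline is a within-patient idea, whereas a t-test on follow-up levels compares different patients and makes no use of where each one started. If follow-up spirometry is correlated with the value before randomisation, part of the variation in the comparison could be removed at no cost in patients.

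A starting value looks feasible. Under Subject Enrollment, patients enter after a 1-month bronchoscopy and a repeat 2 to 3 weeks later, so at about 6 to 7 weeks after transplant.

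What is at stake is the precision of a supportive measure in a trial of 40. Because the measure, the time point and the form of the variable (level or change) are all open, the choice could also be made after the data are seen, by the investigators who run the analysis.

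**Working it through.** **Inputs from the documents.** 20 per arm at target enrolment; significance level from "a 10% stenosis rate in the HBOT group with a p-value of 0.05"; power 80%. Sidedness is not stated and is taken as two-sided.

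**Inputs assumed.** The correlation r between the pre-randomisation and follow-up values is not in the documents, so a range of 0.3 to 0.8 is shown. The SD is taken as equal in both arms and at both times, and the relation between the two values as linear.

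**Step 1: the plan's own figure.** The plan writes "Sample size calculations using a 60% stenosis rate in the usual care group, a 10% stenosis rate in the HBOT group" and concludes that "a sample of 14 subjects/group will have an 80% power to detect statistical significance". With pooled variance and no continuity correction, the mean rate is (0.60 + 0.10)/2 = 0.35 and

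n = [1.960·√(2·0.35·0.65) + 0.842·√(0.60·0.40 + 0.10·0.90)]² / 0.50² = (1.322 + 0.483)² / 0.25 ≈ 13.0, rounded up to 14.

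This matches the plan with a two-sided test. A one-sided calculation with continuity correction also gives 14, so the match is consistent with a two-sided level but does not prove it.

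**Step 2: unadjusted t-test.** The detectable difference δ, in SD units, is the value at which a noncentral t with 2n − 2 degrees of freedom and noncentrality δ·√(n/2) exceeds the two-sided 5% critical value with probability 0.80.

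- n = 20 (38 df): δ = 0.909 SD. Normal approximation: (1.960 + 0.842)·√(2/20) = 0.886.
- n = 14 (26 df): δ = 1.10 SD. This is the case in which the whole margin between 28 and 40 subjects is lost to withdrawal and critical illness.

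**Step 3: ANCOVA.** The residual SD is SD·√(1 − r²) and one degree of freedom is lost. With no correlation at all, the detectable difference is 0.910 SD at 20 per arm and 1.102 SD at 14 per arm, so the lost degree of freedom costs about 0.001 to 0.002 SD. These figures are then multiplied by √(1 − r²). For example, at r = 0.7 and 20 per arm, 0.910·√0.51 = 0.650.

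**Step 4: t-test on change.** The SD of change is SD·√(2(1 − r)), so the figure from step 2 is multiplied by √(2(1 − r)). At r = 0.7 and 20 per arm, 0.909·√0.60 = 0.704.

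| r (assumed) | t-test on level, n = 20 | t-test on change, n = 20 | ANCOVA, n = 20 | t-test on level, n = 14 | t-test on change, n = 14 | ANCOVA, n = 14 |
|---|---|---|---|---|---|---|
| 0.3 | 0.91 | 1.08 | 0.87 | 1.10 | 1.30 | 1.05 |
| 0.5 | 0.91 | 0.91 | 0.79 | 1.10 | 1.10 | 0.95 |
| 0.7 | 0.91 | 0.70 | 0.65 | 1.10 | 0.85 | 0.79 |
| 0.8 | 0.91 | 0.58 | 0.55 | 1.10 | 0.70 | 0.66 |

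All entries are in units of the SD of the spirometric level, n being the number per arm.

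**Step 5: the same gain in other terms.** At 20 per arm, power for a true difference of 0.6 SD is 46% unadjusted, and 57% at r = 0.5, 74% at 0.7 and 87% at 0.8 with ANCOVA. The equivalent unadjusted size, 20/(1 − r²), is 22, 27, 39 and 56 per arm at r = 0.3, 0.5, 0.7 and 0.8.

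**Step 6: chance imbalance.** The standard error of the baseline difference is √(2/20) = 0.32 SD, so an imbalance beyond 0.3 SD in either direction arises in about 34% of such trials. On average a fraction r of it carries through to follow-up: 0.15 SD at r = 0.5 and 0.24 SD at r = 0.8 for an imbalance of 0.3 SD. ANCOVA removes this component.

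**The case against.** Several arguments run the other way.

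- **Validity.** Under randomisation the unadjusted t-test is unbiased, and its standard error already allows for chance baseline imbalance. This stands: the point concerns precision only.
- **Standing of the measure.** Spirometry is neither primary nor secondary. The hypothesis concerns airway complications and the sample size rests on stenosis. This stands, and it limits the weight of the point.
- **What would be tested.** The plan names a test, not the variable. A reader might infer that raw levels will be compared, but a t-test on change or on percent predicted would comply equally. This stands in part. Change scores come close to ANCOVA at r = 0.7 or 0.8, but they gain nothing at 0.5 and are worse than the plain test below it. ANCOVA does not depend on guessing r correctly.
- **The correlation.** It could be low: the baseline would be taken early after transplant, in patients whose plaques have not improved, with follow-up to 12 months. This stands. At r = 0.3 the improvement is only from 0.91 to 0.87 SD.
- **The baseline.** No pre-randomisation spirometry is documented. This stands and makes the fix conditional. If the value is not routinely obtained, the change is an added study measurement and not only a matter of wording.

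A reader might also take 0.91 SD as evidence that stable differences between patients swamp any treatment effect. It is not: 0.91 SD is what any two-group t-test with 20 per arm detects at this level and power, whatever the source of the variation. Nor does the reference to biopsies in each donor lung, under Airway Surveillance, establish a mix of single and bilateral recipients that would drive such differences.

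**Conclusion.** The point holds as a minor one. The plan's rule for continuous data leaves spirometry to a valid but less precise comparison. The cost is the gap between 0.91 SD and the ANCOVA figure at 20 per arm: 0.04 SD at r = 0.3, 0.12 at 0.5, 0.26 at 0.7 and 0.36 at 0.8. At 14 per arm the gap is between 1.10 SD and 1.05, 0.95, 0.79 or 0.66 SD. These sizes rest on a two-sided 5% level, 80% power, complete spirometry in the stated number per arm, and correlations that the documents do not supply.

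It would go too far to conclude that the trial's findings are at risk. No primary or secondary conclusion depends on this analysis.

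**What to change.** Add to Data Analysis and Statistical Considerations, with the measure and time point filled in by the investigators:

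*Spirometric outcomes ([measure] at [time point]) will be compared between the randomised arms by analysis of covariance, with the last spirometry recorded before randomisation as covariate. Where that value is absent, the mean of the recorded baseline values will be imputed and an indicator for missing baseline included.*

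The imputation is acceptable here because the baseline precedes randomisation and so cannot be affected by the assigned arm. Under Measurements and Data Collection, name the same measure and time point and list the pre-randomisation value among the data to be collected.

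The cost is one degree of freedom, or two with the missing indicator, and no added patients. The benefit depends on a pre-randomisation value being on record for most patients, so this should be confirmed first. If r proves low, almost nothing is lost.

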Patients undergo frequent bronchoscopy in the weeks and months following lung transplantation. Many, if not most patients develop some element of necrotic desquamation of the epithelium locally referred to as “exudative plaques” or “pseudomembranes” in the large central airways two to four weeks after lung transplantation. There is a spectrum of involvement, but prior work would suggest that up to 50% of patients who develop the most severe manifestations of these plaques go on to develop some form of large airway complication, most commonly CAS⁹. Our local experience supports this observation. There is no established intervention available for these patients, however, because airway ischemia is thought to play an important role in this process, our group has treated a small group of patients with hyperbaric oxygen therapy (HBOT) with anecdotal improvement in the appearance of the airways as well as a perceived reduction in frequency and severity of anticipated airway complications in some patients.

HBOT is defined as compression of the body with at least 1.4 atmospheres absolute pressure (ATA) of pure oxygen. It is believed to decrease inflammation, control infection, enhance perfusion and promote wound healing.¹⁰ It is used for treatment of chronic refractory wounds, including diabetic, small arterial and radiation-related wounds, as an adjunct to surgical reconstruction wounds, flaps or grafts, and chronic osteomyelitis.¹¹⁻¹³ It has been shown to improve wound healing and decrease the need for limb amputations in diabetic patients. HBOT is not necessary or recommended for normal or uncompromised grafts or flaps, but where the graft or flap is compromised by hypoxia, ischemia or congestion, HBO₂ has been shown to be extremely useful in graft salvage (14). Our preliminary experience with HBOT in lung transplant patients with severe pseudomembranes has been encouraging. We perceive that use of this technique has hastened resolution of the pseudomembranes, improved infectious complications and decreased the incidence of CAS. Based on this preliminary experience we feel systematic examination of this approach is warranted.

OBJECTIVES:

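### The 80% power claimed at 14 per group is 74% under the planned two-sided Fisher's exact test, and it rests on only the most favourable stenosis rates in the protocol

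*Combined protocol and SAP*

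**What the plan says.** Under Data Analysis and Statistical Considerations, the test is fixed first: "Categorical data will be analyzed using Fisher's exact test given the small sample size". The section then gives a 15% stenosis rate among all transplant recipients and adds: "Our clinical experience suggests a rate 2 to 4-fold higher in patients with severe ischemic desquamation". For treated patients it says that "rates of significant airway stenosis may be as low as 10% after therapy". The calculation takes 60% and 10% at a p-value of 0.05, and these figures "suggest that a sample of 14 subjects/group will have an 80% power to detect statistical significance". Neither the formula nor the sidedness is given. The margin above 28 patients is explained as follows: "We will target a total of 40 subjects to allow for subject withdrawal and loss due to the development of critical illness". No expected loss rate is given.

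Two other places bear on this. The Background says that "up to 50% of patients who develop the most severe manifestations of these plaques go on to develop some form of large airway complication" and adds that local experience agrees. Measurements and Data Collection places the sized outcome among the secondary ones ("Secondary outcomes: Include development of airway stenosis"), whereas the primary ones are different: "Primary outcomes: Need for airway stent placement and rate of acute rejection".

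**The concern.** A power statement should describe the test that will be run. Fisher's exact test is conservative in small samples, so a sample size from an uncorrected normal approximation will usually fall short under it. Here the protocol chooses Fisher's test because the sample is small, yet its sample size matches a formula that ignores the small-sample penalty.

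The second issue is the choice of inputs. The usual-care rate is the upper end of a range and the HBOT rate is the lower end of what is hoped for. Together they give the largest difference the protocol can support, and no other pair is examined. If usual care does better than 60%, a non-significant result could be read as evidence against HBOT when the trial had little chance of detecting an effect. A reader could also take the 80% as power for the primary question, which it is not.

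**Working it through.** **Inputs.** Usual care p1 = 0.60, HBOT p2 = 0.10, alpha = 0.05, 14 per group, stated power 80%, Fisher's exact test, 15% base rate with a 2- to 4-fold multiplier (all from Data Analysis and Statistical Considerations); 40 patients at 1:1, so 20 per group (Randomization); up to 50% for any large airway complication (Background). Two-sided testing is assumed because the protocol does not state sidedness.

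**Reproducing the stated 14.** Pooled normal approximation, two-sided, no continuity correction, with mean rate 0.35:

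n = [1.960 × √(2 × 0.35 × 0.65) + 0.842 × √(0.60 × 0.40 + 0.10 × 0.90)]² / (0.60 − 0.10)²

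= [1.960 × 0.6745 + 0.842 × 0.5745]² / 0.25 = (1.8056)² / 0.25 = 13.04, rounded up to **14**.

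So 14 is not a slip in arithmetic. With a continuity correction the same formula gives 16.80, that is 17.

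**Power under the planned test.** For arm sizes n1 and n2, sum Bin(a; n1, p1) × Bin(b; n2, p2) over every outcome (a, b) whose Fisher p-value is at most 0.05. At 60% versus 10%, two-sided, equal arms:

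| Per group | 14 | 15 | 16 | 17 | 18 | 20 |
|---|---|---|---|---|---|---|
| Power | 74.2% | 73.9% | 78.6% | 82.7% | 86.2% | 90.8% |

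The small dip at 15 arises because the test is discrete. One-sided Fisher's test at 14 per group gives 80.7%.

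**How much loss the target of 40 can absorb at 60% versus 10%.** All splits with at most 20 per arm:

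| Evaluable (lost) | Lowest power | Highest power |
|---|---|---|
| 33 to 40 (0 to 7) | 82.7% | above 80% throughout |
| 32 (8) | 78.6% | 86.3% |
| 31 (9) | 75.4% | 84.3% |
| 30 (10) | 73.6% | 81.7% |
| 29 (11) | 72.1% | 80.4% |
| 28 (12) | 67.2% | 79.9% |

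With up to 7 lost, 80% is safe. With 8 to 11 lost, it depends on how losses fall between arms. With 12 lost, which leaves the 28 patients the protocol calls sufficient, no split reaches 80%. If losses fall at random between arms, average power is 82.6%, 78.9% and 76.3% with 8, 10 and 12 lost.

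**Other usual-care rates.** The protocol's range is 15% × 2 = 30% to 15% × 4 = 60%. Two-sided Fisher power against 10% on HBOT:

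| Usual-care rate | 14 per group | 17 per group | 20 per group |
|---|---|---|---|
| 60% | 74% | 83% | 91% |
| 50% | 54% | 63% | 74% |
| 40% | 32% | 39% | 49% |
| 30% | 14% | 19% | 24% |

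At 50% versus 10%, no split of 28 to 40 evaluable patients reaches 80%; the highest is 79.7%, at 19 usual care and 20 HBOT. Equal arms would need 23 per group (81.1%). Turned round, 80% power against 10% needs a usual-care rate of 63.5% at 14 per group, 58.5% at 17 and 52.8% at 20. The first is above the protocol's own maximum.

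**Other HBOT rates.** The protocol gives only 10%. If the rate were 15% or 20% (assumed for illustration), 20 per group would have 79.7% or 65.0% power against 60%.

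**The case against.** Four points can be made for the protocol.

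- **Sidedness is open.** The hypothesis in Objectives is directional. A one-sided formula with continuity correction gives 13.86, also 14, and one-sided Fisher's test has 80.7% power there, so on that reading the statement is right. The same enumeration run one-sided also raises power at 20 per group to 84% for 50% versus 10%, although only to 62% for 40% and 34% for 30%. This stands as a possibility. But nothing in the protocol declares one-sided testing, two-sided is the usual default, and the ambiguity itself needs removing.
- **The trial is sized at 40, not 28.** At 60% versus 10%, 40 patients give 91%, and moderate losses do no harm. The intention-to-treat rule also limits exclusions, although withdrawn patients may still lack outcomes. This stands, and it keeps the test mismatch from being serious on its own.
- **The enrolled group is narrower than the Background's.** Under Subject Enrollment, patients must have grade 3 or 4 plaques and no improvement at a repeat bronchoscopy, so a rate above 50% is possible. But the protocol ties its 2- to 4-fold multiplier to severe desquamation, not to persistence, and never offers this explanation. Both figures are said to reflect local experience, and stenosis alone cannot be commoner than all complications in the same patients. The two figures need reconciling.
- **Fisher's test is a legitimate choice.** Agreed. The criticism is of the power attached to it, not of the test.

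**Conclusion.** The concern holds: the power sentence is wrong as written for the planned test. Under two-sided testing at 0.05, Fisher's exact test has 74% power at 14 per group, not 80%, and equal arms need 17. This shortfall matters little if most of the 40 patients are evaluable and the rates really are 60% and 10%.

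The larger weakness is that those rates are the most favourable the protocol offers and are the only ones examined. Over the rest of its own usual-care range, 30% to 50%, the full target gives 24% to 74% power against 10% on HBOT. All of this concerns stenosis, a secondary outcome; the protocol gives no power for stent placement or acute rejection. The conclusion assumes two-sided testing and independent binomial outcomes. It should be fixed, but it does not by itself call for more patients.

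**What to change.** 1. Replace the power sentence with wording such as: *For stenosis rates of 60% and 10%, two-sided Fisher's exact test at the 0.05 level has 74% power with 14 evaluable patients per group, 83% with 17 and 91% with 20.* This also settles sidedness. Do not state a fixed number of losses the trial can tolerate, because power depends on how losses divide between arms.
2. Reconcile the usual-care rates in the Background and in Data Analysis and Statistical Considerations, giving the reason if 60% is kept for patients with persistent plaques. Report power at 50% and across 30% to 60%, as tabulated above. State that these figures concern stenosis, a secondary outcome, and do not describe power for stent placement or acute rejection.

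Both changes are wording only and need no extra patients. The cost is that the stated power becomes less favourable.
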